## Secondary Hypotheses

- H3:** Total number (ie, including recurrent events) of CV death, HHF, or urgent HF visit in total patient population
- H4:** Time to CV death in patients with LVEF <50%
- H5:** Time to all-cause mortality in patients with LVEF <50%
- H6:** Time to first occurrence of the composite of positively adjudicated sustained  $\geq 50\%$  decrease in eGFR from Baseline (for  $\geq 30$  days), chronic dialysis, renal transplant, or positively adjudicated sustained eGFR <15 mL/min/1.73 m^2 (for  $\geq 30$  days) in total patient population
- H7:** Time to CV death in total patient population
- H8:** Time to all-cause mortality in total patient population

All tests will be two-sided. Significance levels  $\alpha_1 = 0.05$

( $\alpha_2 = \alpha_3 = \alpha_4 = \alpha_5 = \alpha_6 = \alpha_7 = \alpha_8 = 0$ ) are initially defined such that they sum up to  $\alpha = 0.05$ .

The procedure is as follows: Test the hypotheses  $H_i$ ,  $i=1, 2, \dots, 8$ , each at its local significance

level  $\alpha_i$ . If a hypothesis  $H_i$  can be rejected, reallocate its level to other hypotheses according to a pre-specified rule represented by the initial weighted graph. Update the reallocation weights in the reduced graph and repeat the testing step for the remaining, non-rejected hypotheses with the updated local significance levels. This possibility leads to further rejected null hypotheses with the updated local significance levels. The procedure is repeated until no further hypothesis can be rejected.

The reallocation of the local alpha levels is fully determined by the initial graph of the multiple testing strategy.

No further multiplicity adjustments will be made for other efficacy endpoints or subgroup analyses for which nominal p-values may be provided for descriptive purpose only.

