Proportional hazards model for the primary endpoint will be constructed for subgroups defined by the following:

- LVEF in two categories (<50%, ≥50%)
- LVEF in three categories (<40%, ≥40% <50%, ≥50%)
- Region in three categories (The Americas, Europe, Rest of the world)
- Age (<65, ≥65)
- Gender (male, female)
- Race/ethnicity (white, black, Hispanic, Asian, other)
- Baseline eGFR (<60 mL/min/1.73m^2, ≥60 mL/min/1.73m^2)
- Baseline BMI (<30, ≥30 kg/m^2)
- NYHA Class (II, III, IV)
- NT-proBNP (≤Median, >Median)
- MRA at Baseline
- GLP-1 receptor agonist at Baseline
- Sacubitril-valsartan at Baseline
- ICD/CRT at Baseline
- Insulin at Baseline
- Atrial fibrillation or flutter at baseline
- Left ventricular hypertrophy (LVH) at baseline
- Main cause of heart failure (ischemic vs. non-ischemic or unknown)
- Start of first IMP dose prior to vs. after hospital discharge (or urgent care facility where appropriate)

For each factor, a marginal Cox proportional hazard model stratified by region and LVEF (note that when region is the subject of the analysis stratification will only be by LVEF; similarly when LVEF is the subject of the analysis, stratification will only be by region) with non-CV death as a competing event will be constructed, including the treatment, the factor, and the treatment-by-factor interaction terms as covariates. The treatment HR and CI will be estimated from this Cox model for each subgroup. P-values for interaction terms will be provided, and those <0.05 will be considered statistically significant and therefore suggestive of heterogeneity in the treatment effect. Results will be also presented by a forest plot.

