#### ***2.4.4.3 Multiplicity issues***

In order to handle multiple main secondary endpoints, the overall type-I error will be controlled by the use of a sequential inferential approach. Statistical significance of the primary endpoint is required before drawing inferential conclusions about first secondary endpoint at the 0.05 2-sided alpha level. Inferential conclusions about successive secondary endpoints require statistical significance of the prior one. The order of tests is detailed in Section 2.1.3.2 *Secondary efficacy endpoints*. This fixed hierarchical approach will ensure a strong control of the overall type-I error rate at the required 0.05 2-sided level.

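### The SAP labels any of 19 unadjusted subgroup interaction p-values below 0.05 as statistically significant; they should be reported as nominal and descriptive, as the protocol has it

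*SAP*

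**What the plan says.** SAP 2.4.4.1 introduces the subgroup list with "Proportional hazards model for the primary endpoint will be constructed for subgroups defined by the following". Nineteen factors follow. Each gets its own marginal Cox model, "including the treatment, the factor, and the treatment-by-factor interaction terms as covariates". The reading rule is then that "those <0.05 will be considered statistically significant and therefore suggestive of heterogeneity in the treatment effect". The section does not call the results exploratory, adjust them or mention how many tests there are.

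SAP 2.4.4.3 limits its error control to endpoints: "In order to handle multiple main secondary endpoints, the overall type-I error will be controlled by the use of a sequential inferential approach". Interaction tests are outside that sequence.

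Protocol 11.4.2.4 takes a different line. It plans no multiplicity adjustment for other efficacy endpoints or for subgroups, and it refers to "subgroup analyses for which nominal p-values may be provided for descriptive purpose only". Some of the SAP's factors also appear elsewhere in the protocol with a descriptive status. Section 4.4 calls the three-category LVEF analysis exploratory. Sections 9.1.3 and 11.4.2.3 place the LVEF categories and the timing of the first dose relative to discharge among the other endpoints, which are analysed without hypothesis testing. SAP 1.1 says the SAP governs where the documents differ.

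**The concern.** The SAP controls type I error strictly for the primary and ordered secondary endpoints, then gives the same label, statistical significance, to at least 19 uncontrolled tests. With that many tests at 0.05, one flag is the expected result when the treatment effect is uniform.

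The trial stopped enrolling early, and SAP 1.3 says it is not powered for its original assumptions. Interaction tests generally have less power than the main-effect test. Low power does not raise the 5% error rate of each test, but it lowers the share of flags that reflect true heterogeneity. A chance interaction by region, LVEF, age or background drug, presented as significant, could mislead a reader about where the benefit applies.

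**Working it through.** The documents give no family-wise error figure for the interaction tests, so there is no stated figure to reproduce.

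**Inputs**

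- Factors: 19, counted from the list in SAP 2.4.4.1.
- Threshold per test: 0.05, unadjusted (same section).
- Overlap: LVEF appears twice, and the two-category split is nested in the three-category split, so there are 18 distinct characteristics.
- Interaction terms: 15 two-level factors give 15 terms. LVEF in three categories, region and NYHA class give 2 each, and race/ethnicity (five levels) gives 4. Total 15 + 6 + 4 = 25.

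**One independent test per factor, uniform treatment effect**

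- P(at least one p < 0.05) = 1 - 0.95^19 = 62.3%.
- Expected false flags = 19 × 0.05 = 0.95.
- P(two or more) = 24.5% (binomial, n = 19, p = 0.05).
- Counting LVEF once: 1 - 0.95^18 = 60.3%.

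**Correlated tests.** For jointly normal statistics, independence gives the highest value, so correlation lowers it. The documents give no correlations; those below are assumptions (19 equicorrelated two-sided tests, simulated).

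| Assumed rho | P(at least one false flag) |
|---|---|
| 0.1 | 60.6% |
| 0.2 | 57.4% |
| 0.3 | 52.5% |
| 0.5 | 40.9% |

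The expected number of false flags stays at 0.95 whatever the correlation.

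**One p-value per term.** The SAP says "P-values for interaction terms will be provided, and those <0.05 will be considered statistically significant". It does not say whether a factor with more than two levels gets one global test or one p-value per term. Under the per-term reading, independence gives 1 - 0.95^25 = 72.3%, with 25 × 0.05 = 1.25 false flags expected.

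**Check with the SAP's factor structure.** A simulation used the actual number of levels per factor and nested the two LVEF splits. It assumed 1,200 patients and a continuous outcome as a stand-in for the Cox model.

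| Assumed latent factor correlation | One global test per factor | Each term judged separately |
|---|---|---|
| 0 | 63% | 71% |
| 0.2 | 59% | 68% |
| 0.4 | 55% | 63% |

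The 63% is within simulation error of 62.3%.

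**The case against.** The strongest case on the other side has five parts.

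- *The SAP's language is softer than a finding of heterogeneity.* It calls a flag suggestive, and Appendix D puts the primary focus on the overall population. This stands in part. A reader might infer that the plan would announce a false subgroup effect in 62% of trials, or would restrict the population in which benefit is claimed. Nothing in either document ties an interaction result to a decision or a claim. The label of statistical significance is explicit all the same, and that label is the fault.
- *The protocol itself planned no adjustment.* True, and leaving interaction p-values unadjusted is common and defensible. The lack of adjustment is therefore not the error. The error is combining it with a declaration of significance. For the same reason, a 0.05/19 = 0.0026 threshold is not recommended: the protocol planned none, and it would make real interactions harder to see.
- *The protocol let the SAP add subgroups and detail* (section 11.4.2.1, subgroup analysis). True, so the length of the list is not at fault. Both LVEF splits also have a prior basis: the 50% cut is a randomization stratum (protocol 8.4), and the three categories were planned in sections 4.4 and 9.1.3.
- *Appendix D's silence proves little.* Agreed. It lists key changes only. The SAP also refers to a protocol Amendment 2 that is not among the documents, so whether the wording of 11.4.2.4 was still in force cannot be confirmed. An undisclosed reversal cannot be inferred.
- *62% is one scenario.* It assumes one independent test per factor. The other scenarios shown run from 41% to 72%.

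**Conclusion.** The concern holds as a wrong reading rule for the subgroup analyses. Under a uniform treatment effect, the SAP's rule yields at least one false flag with probability of about 62% for one independent test per factor. The figure is about 41% to 61% at assumed correlations of 0.5 to 0.1, and up to about 72% if all 25 terms are judged separately. About one false flag is expected with one test per factor. These figures rest on each test holding its 5% level; the correlations are assumed.

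A reader might take this to mean that the trial's type I error is inflated. It is not: the primary test and the ordered secondary tests use none of this alpha and are unaffected. The point should be corrected before the subgroup results are reported, but it does not threaten the main conclusion.

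**What to change.** In SAP 2.4.4.1, delete the clause that confers statistical significance on interaction p-values below 0.05. Replace it with text along these lines: *Subgroup hazard ratios, confidence intervals and interaction p-values are nominal and descriptive. Each factor, including those with more than two levels, has one global interaction test. With 19 factors, about one interaction p-value below 0.05 is expected by chance when the treatment effect is uniform. The two LVEF splits overlap and are not independent evidence.*

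Keep both LVEF splits and the forest plot, and set no Bonferroni threshold.

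The cost is a few SAP sentences. No data or hazard ratio estimates change. The downside is that a real interaction is described, with its estimate, interval and p-value in view, and not declared significant.

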#### ***2.4.4.2 Analyses of secondary efficacy endpoints***

Methods for controlling the overall type-I error rate when testing the secondary efficacy endpoints are described in Section 2.4.4.3 *Multiplicity issues*.

Time-to-event secondary efficacy endpoints will be analyzed using the same statistical methodology as for the primary endpoint. Deaths that are not part of a given endpoint will be treated as competing events.

As with the primary endpoint, the absolute risk reduction (ARR) of time-to-event secondary endpoints will be estimated by the difference between treatment groups in the number of events per 100 patient-years of follow-up. For those secondary endpoints which are a composite of events, results will be provided for both the overall composite and its individual components.

Absolute change in KCCQ-12 scores from baseline to Month 4 will be analyzed by analysis of covariance (ANCOVA) with treatment group as factor and baseline KCCQ-12 score and randomization stratification factors as covariates. The last available post-baseline score will be

carried forward to Month 4 if the patient is alive at Month 4 but the Month 4 value is missing. For patients who die, a worst score (0) will be imputed for the clinical summary score at all subsequent scheduled visits after the date of death where the clinical summary score would have been assessed.

The rate of decline in eGFR observed over time will be analyzed by repeated-measures mixed-effects models with absolute change in eGFR from baseline as the outcome, a random effect for intercept, and fixed effects for treatment, baseline value, and time. An additional model will be developed with an interaction between treatment and time. The variance-covariance matrix will be specified to be unstructured.

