### **9.1.3 Other efficacy endpoints**

All the following endpoints are assessed in the total patient population:

- Proportion of patients with HHF or urgent HF visit (see [Appendix B](#)) within 30 days of Randomization
- Changes in KCCQ-12 scores from Baseline to Week 2, Month 1, Month 4, Month 8, Month 12, then annually
- Time to  $\geq 50\%$  decrease in eGFR from Baseline
- Proportion of patients with  $\geq 1$  new onset of atrial fibrillation, atrial flutter, or ventricular arrhythmia from Randomization
- Time to first MI (fatal and nonfatal)
- Time to first stroke (fatal and nonfatal)
- Changes from Baseline to Month 1 and Month 4 for NT-proBNP
- Changes from baseline in loop diuretics at day 180 and/or end of treatment visit
- Changes in hemoconcentration from Baseline at Week 2, Month 1, Month 4, Month 12, and EOT
- Changes from Baseline to Month 4, Month 12, and Month 24 in:
  - Hemoglobin A1c
  - Body weight

- Time to first occurrence of either of the following clinical events in subgroups of patients who started first IMP dose prior vs. after hospital discharge (or urgent care facility where appropriate):
  - Cardiovascular death
  - Hospitalization for heart failure

The following endpoints are assessed in subgroups of patients defined by LVEF:

- Time to first occurrence of either of the following clinical events in patients with LVEF <40%:
  - Cardiovascular death
  - Hospitalization for heart failure
- Time to first occurrence of either of the following clinical events in patients with LVEF  $\geq$ 40% to <50%:
  - Cardiovascular death
  - Hospitalization for heart failure
- Time to first occurrence of either of the following clinical events in patients with LVEF  $\geq$ 50%:
  - Cardiovascular death
  - Hospitalization for heart failure
- Time to all-cause mortality in patients with LVEF <40%
- Changes in hemoconcentration from Baseline at Week 2, Month 1, Month 4, Month 12, and EOT in patients with LVEF <40%

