### 1.2.2 Secondary objectives

The secondary objectives of the study are to compare the effects of sotagliflozin to placebo on:

- The total occurrences of HHF and urgent visit for HF
- The occurrence of CV death
- The occurrence of all-cause mortality
- The total occurrences of CV death, HHF, urgent visit for HF, non-fatal myocardial infarction (MI), and non-fatal stroke
- Change in KCCQ-12 score
- Change in estimated glomerular filtration rate (eGFR)

[figure not shown]

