### ***2.1.3.2 Secondary efficacy endpoints***

- Total occurrences (first and potentially subsequent) of HHF and urgent HF visits
- Time from randomization to occurrence of CV death
- Total occurrences (first and potentially subsequent) of CV death, HHF, non-fatal myocardial infarction, and non-fatal stroke
- Total occurrences (first and potentially subsequent) of HHF, urgent HF visit, CV death, and HF while hospitalized
- Time from randomization to all-cause mortality
- Change in KCCQ-12 scores from baseline to Month 4
- Rate of decline in eGFR after Week 4 (mL/min/1.73m^2/year) to the end of the study

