### Scoring the KCCQ-12

Four domain scores and one summary score are generated from the KCCQ-12:

Physical Limitation Score	(KCCQ12-PL)
Symptom Frequency Score	(KCCQ12-SF)
Quality of Life Score	(KCCQ12-QL)
Social Limitation Score	(KCCQ12-SL)
Summary Score	(KCCQ12)

Scores are scaled 0-100, where 0 denotes the lowest reportable health status and 100 the highest.

---

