**Summary Score**

The Summary score represents an integration of the patient’s physical limitation, symptom frequency, quality of life and social limitation. If all four domain scores are missing, no summary score is computed. Otherwise, the score is calculated as the average of the non-missing domain scores:

$$KCCQ12 = average of KCCQ12-PL, KCCQ12-SF, KCCQ12-QL and KCCQ12-SL$$

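### The Month 4 KCCQ-12 test carries early-recovery scores forward in survivors and, for patients closed out before Day 85, scores deaths 0 while leaving survivors missing

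*SAP*

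**What the plan says.** SAP 2.1.3.2 lists "Change in KCCQ-12 scores from baseline to Month 4" as the sixth of seven ordered secondary endpoints. SAP 2.4.4.3 puts all seven in a fixed sequence: "Inferential conclusions about successive secondary endpoints require statistical significance of the prior one".

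SAP 2.4.4.2 analyzes absolute change by ANCOVA and gives two filling rules:
- **Survivors:** the last post-baseline score is "carried forward to Month 4 if the patient is alive at Month 4 but the Month 4 value is missing".
- **Deaths:** a score of 0 is "imputed for the clinical summary score at all subsequent scheduled visits after the date of death where the clinical summary score would have been assessed".

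SAP 2.5.3 adds a general default: where the endpoint assessment is missing, so is the change from baseline.

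The schedule in Protocol 9.1.3 is "Changes in KCCQ-12 scores from Baseline to Week 2, Month 1, Month 4, Month 8, Month 12, then annually". The flow chart (Protocol 1.2) also has a KCCQ-12 at the premature end-of-treatment (pEOT) visit and at the Study Closeout Visit.

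On naming, SAP 1.2.2 says only "Change in KCCQ-12 score". SAP Appendix B states: "Four domain scores and one summary score are generated from the KCCQ-12". It defines the summary score so that "the score is calculated as the average of the non-missing domain scores". No clinical summary score is defined.

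**The concern.** There are two substantive problems and one editorial one.

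1. **Carry-forward.** Patients enter during or just after an admission for worsening heart failure, and the dose may be raised from Day 15. Health status is likely to be moving between Week 2 and Month 4. Carrying an early score to Month 4 assumes it stands still, and the plan has no sensitivity analysis for that assumption.
2. **Early closeout.** Enrollment ended in March 2020 (SAP 1.1), and sites were told to complete end-of-study contacts on 1 May 2020 (SAP 2.4.4.4). Some patients could not have reached the Month 4 window. If survivors in that group are missing and deaths score 0, the group contributes only zeros to a hierarchically tested comparison.
3. **Name of the score.** The endpoint does not say which of five scores is tested, and the death rule uses a name that Appendix B does not define.

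**Working it through.** **The window.** SAP 2.5.4 gives Month 4 as target Day 113, Days 85 to 141. This reproduces: 16 × 7 + 1 = 113, and 113 ± 28 = 85 to 141.

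**What is carried forward.** The scheduled earlier scores are at Day 15 and Day 29. The distances to the target are 113 − 15 = 98 days and 113 − 29 = 84 days. The Week 4 window ends at Day 36 and Month 4 opens at Day 85, so Days 37 to 84 (48 days) belong to no window. A pEOT or closeout score taken there can reach the test only by being carried forward. A closeout score on Days 85 to 141 counts as Month 4, so only closeout before Day 85 is at issue.

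**Effect of carry-forward on the arm difference.** With a fraction m carried, the estimated difference is (1 − m) × d4 + m × d1, where d1 and d4 are the early and Month 4 differences. The documents give none of these. Assumed values for illustration:

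| Pattern | d1 | d4 | m = 5% | m = 20% |
|---|---|---|---|---|
| Growing | 2 | 4 | 3.9 | 3.6 |
| Waning | 4 | 2 | 2.1 | 2.4 |
| Stable | 4 | 4 | 4.0 | 4.0 |

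**Who cannot reach Day 85.** Randomization is Day 1, so Day 85 is randomization + 84 days. With a last contact on 1 May 2020, the latest randomization date that reaches it is 7 February 2020. Actual accrual is not in the documents. Assume uniform accrual, a start between 5 January and 17 December 2018 (the two protocol version dates, not first-patient dates), and a close between 1 and 31 March 2020:

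| Last contact | Start | Close | Days after cut / accrual days | Share |
|---|---|---|---|---|
| 1 May | 5 Jan 2018 | 1 Mar 2020 | 23 / 786 | 2.9% |
| 1 May | 1 Jul 2018 | 15 Mar 2020 | 37 / 623 | 5.9% |
| 1 May | 17 Dec 2018 | 31 Mar 2020 | 53 / 470 | 11.3% |
| 31 May (cut 8 Mar) | 5 Jan 2018 | 1 Mar 2020 | 0 / 786 | 0% |
| 31 May (cut 8 Mar) | 17 Dec 2018 | 31 Mar 2020 | 23 / 470 | 4.9% |

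With contacts to 30 June 2020 the cut is 7 April 2020, after enrollment closed, and the share is 0%.

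**Which rule applies to them.**
- **Survivors.** The carry-forward rule requires the patient to be alive at Month 4. That cannot be established when contact ended earlier, so the SAP 2.5.3 default applies and the change is missing.
- **Deaths.** Month 4 is a scheduled visit after the death, so the natural reading is 0. The closing qualifier of the death rule also allows the reading that no assessment was due.
- **Together.** On the natural readings, a late-randomized patient enters the ANCOVA only by dying.

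**Precision of the fix.** Relative to fully observed Month 4 data, with correlation ρ between the earlier and Month 4 scores (assumed 0.5 to 0.7) and a fraction p imputed, the standard error ratio is √(1 + (1 − ρ²) × p/(1 − p)):
- p = 2.9%, ρ = 0.7: √(1 + 0.51 × 0.030) = 1.008
- p = 11.3%, ρ = 0.5: √(1 + 0.75 × 0.127) = 1.047

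Leaving the same patients missing gives 1/√(1 − p) = 1.015 to 1.062.

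**The case against.** The strongest defense is that the text already settles early closeout. A patient last seen before Day 85 does not meet the alive-at-Month-4 condition, so SAP 2.5.3 makes the change missing, and a death scores 0. That reading is fair. It does not remove the problem, because it is exactly the combination that lets outcome decide who is analyzed.

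It can also be said that LOCF was prespecified, that a closed-out patient would often have a closeout score later than Month 1, and that the shares rest on assumed accrual. The last two points stand. They are why no point shift is claimed for the closed-out group, and the upper end of the range may be high, since SAP Appendix D describes enrollment after Amendment 2 as very limited. Prespecification fixes the method but does not make a Day 15 score a Month 4 score.

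Three stronger readings are tempting and are not supported:
- **The plan tests the wrong score.** The tested score is unnamed. The odd name occurs only in the death rule, and Appendix B has a single summary score, which is almost certainly meant. No numerical shift is expected.
- **LOCF favors sotagliflozin or inflates type I error.** The direction depends on whether the effect grows or wanes. With no effect at any time, late randomization gives no reason to favor either arm.
- **LOCF only dilutes.** A waning effect is inflated, as the table shows.

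**Conclusion.** The point holds and should be corrected, but its reach is modest. LOCF normally replaces a missing Month 4 score with one from 84 or 98 days before the target day. In the illustration, a true difference of 4 becomes 3.9 to 3.6 if the effect is growing, and a true difference of 2 becomes 2.1 to 2.4 if it is waning. Both rest on assumed differences and on 5% to 20% of scores being carried.

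The closed-out group is 0% to about 11% of patients, depending on assumed accrual and on whether 1 May 2020, which the SAP gives only for days alive and out of hospital, was the true last contact. Inclusion that depends on death is a flaw at any nonzero share.

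Only the KCCQ-12 step and the eGFR step after it are affected, and they become inferential only if the primary and the first five secondary endpoints are significant. The naming issue is clerical and would not justify a change by itself.

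**What to change.** - **Survivors without a Month 4 value.** Make multiple imputation by arm the primary method. Use baseline, Week 2, Month 1 and any later pre-window score (pEOT or closeout) with its timing, then run the planned ANCOVA. Keep LOCF as a sensitivity analysis. State that missing at random is an assumption for missed visits.
- **Patients randomized too late to reach Day 85.** Define the group by randomization date. Keep known deaths at 0, because their Month 4 status is known and should not be overwritten. Impute the survivors from same-arm patients still alive at the same study day, with later deaths before Month 4 scored 0 among those donors. Add a sensitivity analysis restricted to patients randomized early enough to reach the window.
- **Editorial.** Name the Appendix B Summary Score (KCCQ12) in SAP 1.2.2, 2.1.3.2 and 2.4.4.2, including the death rule.

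The cost is SAP wording, one imputation program and the wider standard error shown above. The gain is an estimate of Month 4 status with inclusion that does not depend on outcome; it is not a gain in power.
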